4.10 Data analysis

A mixed methods analytic approach will be applied.

4.10.1 Quantitative analysis

Descriptive statistics will be calculated for all study variables. Continuous variables will be reported using the appropriate measure of central tendency. Categorical variables will be summarized as proportions. Analyses will be conducted using SAS and R. The primary and secondary outcomes will be analysed with multivariable regression models adjusted for age, comorbidity count, prior primary care utilisation in the 3 years prior to enrolment and Socio-Economic Indexes for Areas (SEIFA). Sub-group analyses will be conducted to examine variation in outcomes for the cohort to assess a range of demographic and clinical characteristics.

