3.1 Background to community pharmacy prescribing

On an international and national basis, the scope of practice for community pharmacists is evolving rapidly. The NSW and ACT Governments have recognised this expanded role community pharmacists could play. The broad approach is to increase the community's access to primary care through:

- 1. Authorising pharmacists to administer a wider range of public health and travel vaccinations from 14 November 2022, including Japanese Encephalitis, Hepatitis A and Hepatitis B, Poliomyelitis, Typhoid and Zoster.
- 2. Funding a 12-month trial to evaluate allowing pharmacists to manage uncomplicate urinary tract infections in a specified cohort of females.
- 3. Funding a 12-month trial to evaluate allowing pharmacists to extend the supply of certain low risk oral contraceptive pills (OCPs).
- 4. Supporting a state-wide trial where appropriately trained pharmacists can prescribe medications for certain conditions, such as skin ailments [7].

This study protocol refers to the third goal above.

Contraception plays a pivotal role in the well-being and health of women permitting individuals control over their sexuality, fertility, and reproductive choices [8]. The public health and development impact of contraception is well established and so profound that access to contraception is now considered an essential element of the human right to health in the international community [8]. Contraception improves birth outcomes, slows population growth, and improves socioeconomic status [8]. Despite the proven effectiveness and benefits of contraception, advances in contraceptive technology, and the recognition of contraceptive access as a basic human right, the international community is said not to have achieved universal access to contraception [8].

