4.6.5 Medicare Benefits Schedule (MBS) and Pharmaceutical Benefits Scheme (PBS) data

Participants will be requested at registration to provide consent to access their MBS and PBS data for the evaluation. The Services Australia approved patient and information consent form (Appendix 23) will be used to seek consent. Participants will have the option of authorising Services Australia to provide their claim history for MBS, PBS or both.

As the study will be examining how the use of this service impacts consistency of oral contraception adherence, a 3-year lookback will be requested for PBS data. This will allow analysis of prescribing and dispensing habits over multiple prescribing and refill cycles and to assess discontinuation rates pre and post introduction of the service as a proxy to assessing adherence gaps.

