4.9 Outcomes

Primary outcomes

Primary outcomes will be accessibility and acceptability of the service (based on self-report at 7-day follow up). This will be a composite measure based on patient self-reported data. It includes seven items adapted from existing questionnaires, including a validated questionnaire for perceived service quality in community pharmacies (two items) and studies of pharmacy prescribing for oral contraception, and other medications [1-6]. It will cover the following domains: (a) trust and confidence in health and medical advice provided, (b) convenience, (b) privacy during discussion with pharmacy, and (b) overall satisfaction. Each item is scored on a 7-point Likert scale. Each domain will be equally weighted, and an aggregated score calculated and scaled to a maximum score of 100.

Secondary outcomes

- **On time dispensing rates**: 36 months pre and 12 months post introduction of the intervention (assessed using the proportion of days covered method using PBS data) [40].
- **Primary care utilisation:** MBS records will be used to measure use of general practice services prior up to 36-months pre and 12 months post introduction of the intervention date (MBS data).
- **Safety outcomes**: Adherence rates to Clinical management protocols (assessed by practice change facilitators conducting regular pharmacy monitoring and inspection of data from the patient consultation IT system), hospitalisation for potential pill-related adverse events (e.g., thromboembolic disease) (NSW Health data), rates of STI tests undertaken (MBS pathology data) and adverse events.
- **Implementation outcomes**: Implementation outcomes will also be assessed to examine the fidelity, reach and adoption of the new service, and barriers and facilitators to implementation.

• **Economic outcomes:** Results from the economic analysis will be expressed as (1) net benefit in terms of implementation costs and cost savings arising from more efficient treatment pathways; and (2) cost-consequence results accounting for patient experience measures, relevant safety outcomes and implementation measures. This will be assessed using multiple data sources including MBS records for 36 months pre and 12 months post introduction of the intervention.

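### GP use, pill dispensing and MBS costs are compared before and after the service with no comparator and no calendar-time term, so any pre/post difference includes about 24 months of background change

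*Protocol*

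**What the plan says.** Three groups of secondary outcomes in Protocol 4.9 use the same long-before, short-after windows.

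- **On-time dispensing:** "36 months pre and 12 months post introduction of the intervention (assessed using the proportion of days covered method using PBS data").
- **Primary care use:** "MBS records will be used to measure use of general practice services prior up to 36-months pre and 12 months post introduction".
- **Economic outcomes:** several data sources, including "MBS records for 36 months pre and 12 months post introduction of the intervention".

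Section 4.6.5 gives the purpose of the three-year PBS lookback: to "assess discontinuation rates pre and post introduction of the service as a proxy to assessing adherence gaps". Section 4.2 describes one cohort, and no section provides a comparison group or external series.

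For analysis, 4.10.1 states: "The primary and secondary outcomes will be analysed with multivariable regression models adjusted for age, comorbidity count, prior primary care utilisation" over the three years before enrolment, and SEIFA. Calendar time, season and pre-period slope are not mentioned anywhere. Section 4.10.3 reports net benefit, including cost savings, with bootstrapped uncertainty intervals.

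The protocol uses two anchors in time. Section 4.9 dates its windows from introduction of the intervention, while the covariate in 4.10.1 is dated from enrolment. Whether introduction means the trial start or each woman's own registration is not stated.

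**The concern.** With one cohort and no comparator, the only evidence on whether the service changed GP visits, dispensing or costs is the difference between the two windows. Comorbidity count, SEIFA and prior GP use are one value per woman, so they cannot represent change between windows. Age can be updated, but it does not track background change either. For GP use, the prior-use covariate is the outcome's own pre-period, so it cannot serve as a control for trend.

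A background fall in GP visits would then look like visits saved and pass into the net-benefit result. A background rise would hide a real saving. The same applies to days covered and discontinuation. Bootstrap intervals reflect sampling variation only, so a shifted saving could still look precise. The primary outcome, a day-7 questionnaire score, has no pre-period and is unaffected.

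**Working it through.** The protocol states no trend, effect size or sample size for these outcomes, so there is no figure of its own to reproduce.

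**1. Gap between windows (4.9).** Pre-window midpoint: (-36 + 0)/2 = -18 months. Post-window midpoint: (0 + 12)/2 = +6 months. Gap: 6 - (-18) = 24 months.

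**2. Size of the shift with no service effect.** Let g be an assumed constant annual trend. The pre/post rate ratio is approximately (1 + g)^(24/12) = (1 + g)^2. Averaging monthly rates over the actual windows gives almost the same result.

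| Assumed g per year | (1 + g)^2 | Averaged over windows |
|---|---|---|
| -10% | 0.810 | 0.807 |
| -5% | 0.903 | 0.902 |
| -2% | 0.960 | 0.960 |
| +2% | 1.040 | 1.040 |
| +5% | 1.103 | 1.102 |
| +10% | 1.210 | 1.206 |

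For an outcome that drifts linearly, such as days covered, the shift is 2 times the annual change: 1 percentage point per year gives 1 × 24/12 = 2 points.

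**3. Whether the named covariates remove it.** This was simulated with 4,000 women, entry spread over 12 months, about 4 GP visits per woman-year, no service effect, and a two-period Poisson model with all four covariates (all inputs assumed).

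- Age at enrolment: ratio 0.91 at -5% per year and 1.12 at +5%.
- Age updated by period: 0.90 and 1.11 (0.904 and 1.105 before rounding).
- Monthly data with a linear calendar term, a post-registration step, age, comorbidity count and SEIFA: 1.006 and 1.005.

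The covariates leave the shift in place. The last line shows recovery, but that simulation did not select women on the eligibility rules.

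**4. Whether a trend plus a step is safe here.** Section 4.4.2 requires a prescriber review in the last 2 years and 2 continuous years on the same pill. The review requirement raises GP use in the 24 months before registration. A linear time term can read that rise as an upward trend, project it into the post period and push the step further down. With women selected on a review in the previous 24 months, no service effect and no background trend:

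| Analysis | Rate ratio (true value 1.00) |
|---|---|
| Raw pre/post | 0.95 to 0.98 |
| Linear calendar time + step | 0.90 to 0.95 |
| Calendar-month effects + step | 0.92 to 0.97 |

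With calendar time plus a separate indicator for each pre-registration year, post against months -36 to -25 gave 0.97 to 1.02 across trends from -5% to +5% per year.

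**5. Whether the anchor matters.** If introduction is one common calendar date, 48 month effects and a post indicator make 49 columns of rank 48, so the service effect cannot be separated from time. Dating from each woman's registration gives staggered entry and removes that exact collinearity.

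**The case against.** **No pre/post model is written.** Section 4.10.1 gives no post term, link function or unit of analysis. Its prior-use covariate would fit equally well in a model of the post-period outcome given baseline, which has no pre/post coefficient. A SAP could also add a time term. This stands: the contrast is inferred, and a reader might go too far by concluding that the protocol commits to a regression coefficient that absorbs trend. However, 4.6.5 names a before/after assessment, 4.10.3 needs a saving relative to something, and the protocol names its adjustment variables without one for time.

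**No trend is documented.** This also stands. A reader might infer that the wider vaccination role, "Authorising pharmacists to administer a wider range of public health and travel vaccinations from 14 November 2022", lowered GP use in these women. Section 3.1 presents it as a measure to widen access to primary care, but gives no effect on GP visits at ages 18 to 35 or on pill dispensing. It shows that services were changing, not by how much.

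**Costs follow another route.** Section 4.10.3 values MBS use at current listed prices, which removes price trend, and bootstraps net benefit rather than using the 4.10.1 regression. That narrows the point to trend in the volume of use. The bootstrap route has no adjustment for that either.

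**A time term can do harm.** Step 4 of the working bears this out, and it determines the form of the fix.

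**Conclusion.** The concern holds for GP use, on-time dispensing, discontinuation and the MBS volumes behind net benefit. Any before/after difference in these includes about 24 months of background change, and the adjustment named in 4.10.1 does not remove it. The 24 months follows from the protocol's own windows. The resulting size, about 4% at 2% per year and about 10% at 5% per year in either direction, rests wholly on assumed trends.

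It would be tempting to quote false-positive rates. The documents do not support that, because 4.9 and 4.10 set no test, significance level or sample size for these outcomes. Nor do they show which way the bias would run. These are secondary outcomes, but they carry the economic conclusion, so the analysis should be changed before the MBS and PBS data are analysed.

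**What to change.** In 4.10.1, for GP use, on-time dispensing, discontinuation and MBS costs:

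1. Date the windows from each woman's registration, and say so in 4.9.
2. Analyse the dated MBS/PBS records by woman-month, with standard errors clustered by woman.
3. Include calendar time (month effects, or a linear trend with season) together with indicators for time relative to registration: months -36 to -25, -24 to -13, -12 to -1, and post. Keep age, comorbidity count and SEIFA.
4. Do not make a single linear trend plus step the main result.
5. Report the post estimate against each pre-registration year, so that the effect of the review requirement is visible.
6. For GP use and costs, omit the three-year prior GP-use covariate, which is the pre-period outcome.
7. For days covered and discontinuation, use only months after each woman's first recorded supply, because the early pre-period includes women who had not yet started the pill.
8. Label the raw pre/post difference descriptive, and show net benefit under both the adjusted and the raw estimate.

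The cost is analysis wording and programming. The MBS and PBS histories are already being requested, but the extract dates should be checked to cover both windows around each registration. Intervals will be wider, by an amount not quantified here. The result also assumes that women who register at different times are otherwise comparable.

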4.4.1 Participant consent

All participants will require informed consent. Participants will be provided with two consent forms (one for the study and a second form from Services Australia allowing access to MBS and PBS data). They will be given the option of separate consent. The pharmacist will provide the participant with a location specific QR code for scanning on their mobile phone. This will open a secure webform hosted by the George Institute. The participant will then enter their personal details and be asked to review and tick the boxes. They will then provide a finger signature on a signature panel on the screen and click submit for secure submission to The George Institute. The participant will be sent an SMS or email confirmation message with a validation code which they will provide to the pharmacy.

If participants wish to withdraw from the study once it has started, they can do so at any time without having to give a reason. Withdrawing from the study will not affect their relationship with their employers, professional organisations, care providers or receipt of any care or treatment. Participants wishing to withdraw should notify their pharmacist or one of the research team. Once a participant decides to withdraw from the study, no further information will be collected from them. Their information will be removed from study records and will not be included in the study results.

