4.10.3 Economic analysis

The analysis will be conducted from a health service perspective (base case) and a societal perspective including direct and indirect costs from the health-consumer's perspective - out of pocket expenses for any medicines or products provided, waiting time and travel time to attend treatment, productivity gains or time lost from work.

The scope of the within-study cost analysis is constrained by the design of the cohort study. Cost items associated with the co-design process, research and evaluation will be excluded. Resource use associated with the 2 components, pharmacy enrolment, training and support and pharmacy consultation, will be prospectively identified, measured and valued. In measuring resource use associated with delivery of the intervention, data will be collected from the research team, from the enrolled pharmacies and from the enrolled patients. Labour time will be measured using opportunity costs and valued based on Pharmacy Industry Award rates of pay, and average earnings for patients.

Health care resource use will be captured per the secondary outcomes of the study. Primary care resource use will be measured from MBS records and valued based on current Medicare Benefits Schedule listed prices. Medication use will be valued using Pharmaceutical Benefits Schedule listed prices, over-the counter medication will be valued using market prices. Hospital utilisation will be measured using the APDC and EDDC and valued based on Independent Health and Aged Care Pricing Authority (IHACPA) National Efficient Price tariffs.

Results from the economic analysis will be expressed as (1) net benefit in terms of implementation costs and cost savings arising from more efficient treatment pathways; and (2) cost-consequence results accounting for patient experience measures, relevant safety outcomes and implementation measures.

Decision uncertainty will be accounted for using parametric and non-parametric bootstrapping to generate uncertainty intervals around the net benefit result.

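### The adjusted analysis of the Day-7 survey score requires a covariate that the protocol can obtain only from women who give a separate, optional MBS consent

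*Protocol*

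**What the plan says.** Section 4.10.1 gives one covariate list for outcomes of different origin. Both the primary and the secondary outcomes get "multivariable regression models adjusted for age, comorbidity count, prior primary care utilisation in the 3 years prior to enrolment and Socio-Economic Indexes for Areas" (SEIFA).

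Section 4.9 describes the primary outcome, a score scaled to a maximum of 100 and collected at the 7-day follow-up: "This will be a composite measure based on patient self-reported data".

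For GP use, section 4.9 says "MBS records will be used to measure use of general practice services prior up to 36-months pre and 12 months post introduction" of the intervention, and section 4.10.3 says "Primary care resource use will be measured from MBS records". No other source of GP use is named.

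Section 4.4.1 describes two consent forms, one for the study and one from Services Australia, and adds: "They will be given the option of separate consent". Section 4.6.5 lets the woman narrow the second form further: "Participants will have the option of authorising Services Australia to provide their claim history for MBS, PBS or both".

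Section 4.4.2 does not make MBS consent an inclusion criterion. Section 4.6.2 sends the Day-7 survey to those assessed as eligible, with no condition on linkage consent.

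**The concern.** The covariate and the outcome come from different groups of women. The outcome exists for everyone who answers the Day-7 survey. The covariate exists only for those who also sign the second form and include MBS in it. The regression for the primary outcome therefore asks for something that some responders lack because of the consent design, not through chance missingness.

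Two things are at stake. The first is precision, because responders who gave a complete survey leave the adjusted analysis. The second is selection. Willingness to share Medicare records may be related to trust, and trust and confidence in the advice given is one of the four scored domains. That link is plausible, but the protocol neither documents it nor gives its direction.

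**Working it through.** **Reproducing a stated figure.** There is none to reproduce. The protocol gives no MBS consent rate and no survey response rate. The check is a trace of data sources, followed by an illustration on assumed values.

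**Trace**
1. Outcome: Day-7 self-report score (section 4.9). Linkage needed: none.
2. Covariate: primary care use over 3 years before enrolment (section 4.10.1). That section does not name its source. Sections 4.9 and 4.10.3 name MBS for GP use, and the 36-month pre-period in section 4.9 matches the 3 years, so MBS is the natural reading.
3. Other possible sources: the items pharmacists record (section 4.6.1) include no GP visit history. Section 4.6.2 mentions only basic demographic and clinical information at registration. The eligibility criterion of a GP review in the last 2 years is a yes/no condition that every participant meets, not a measure of use. NSW Health data supply hospital and emergency department use in section 4.10.3, not GP use.
4. Access: a separate form that can be declined, or signed for PBS only (sections 4.4.1 and 4.6.5).
5. Follow-up: not conditional on step 4 (section 4.6.2).

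Steps 1 to 5 together allow a responder with a valid outcome and no covariate.

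**Illustration (assumed inputs).** Let c be the share of Day-7 responders who authorise MBS. With a complete-case fit and the same residual spread in both groups:
- responders lost = 1 − c
- standard error (and CI width) multiplied by 1/√c
- shift in the mean relative to all responders = (1 − c) × D, where D is the mean score of consenters minus that of non-consenters. D = 5 points is an assumption, and its sign could be either.

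| c | Responders lost | 1/√c | Shift if D = 5 |
|---|---|---|---|
| 0.95 | 5% | 1.026 | 0.25 |
| 0.90 | 10% | 1.054 | 0.50 |
| 0.80 | 20% | 1.118 | 1.00 |
| 0.70 | 30% | 1.195 | 1.50 |
| 0.50 | 50% | 1.414 | 2.50 |

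If no covariate depends on MBS, c no longer enters: nobody is lost for lack of MBS consent and the factor is 1.00.

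**The case against.** **The descriptive analysis already uses everyone.** Section 4.10.1 first plans descriptive statistics for all study variables, so the score will be summarised in all responders. This stands. A reader might infer that the study's answer on acceptability becomes an answer only for women willing to share Medicare data. The protocol does not support that, because only the adjusted analysis is affected. What remains is that section 4.10.1 assigns the analysis of the primary outcome to the regression and does not say which of the two results is primary.

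**The loss presumes complete cases.** Section 4.10.1 does not specify a complete-case fit, and a statistical analysis plan could impute or use a reduced model. This also stands, and the absence of a missing-data rule is not the point here. The point is that the protocol fixes, for a survey outcome, a covariate that some responders lack by design. A later plan would have to work around that.

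**The covariate might be harmful elsewhere.** A reader might infer that adjusting for prior GP use distorts the GP-use outcome, since the same visits would be both covariate and pre-period. The documents do not support this. Sections 4.9 and 4.10.1 specify no before-after model. If post-period use is modelled, conditioning on pre-period use is ordinary baseline adjustment. If pre and post records are stacked with complete pairs, a woman-level covariate leaves the period contrast unchanged.

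**A single-arm regression has no purpose.** This too might be inferred, since there is no exposure contrast to adjust. Describing how acceptability varies with patient characteristics is a legitimate aim, and section 4.10.1 says variation in outcomes will be examined. The regression is not an error in itself.

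**The size is assumed.** True. At 95% consent the effect is small, and the protocol states no acceptability threshold that a shift could cross.

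**Conclusion.** The point holds for the regression of the primary survey score: as written, it requires a covariate that an eligible, responding participant may lack because she used a consent option the protocol gives her. Fitted on complete cases, it excludes all such responders from an analysis whose outcome needs no linkage.

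The size cannot be found from the protocol. For MBS consent between 50% and 95%, the standard error rises by about 41% to 3%. Any shift in the mean depends on an unknown difference between consenters and non-consenters.

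The conclusion rests on MBS being the source of the covariate, which is inferred from sections 4.9 and 4.10.3, and on a complete-case fit. The appendices, including the follow-up form, are not at hand. If GP use is in fact also collected by self-report, the protocol should say so and the point falls away. The conclusion does not extend to the descriptive summary or to the GP-use outcome.

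**What to change.** In section 4.10.1:
- Name the mean composite score with its 95% CI, in all Day-7 responders, as the primary result.
- Restrict the regression for the survey outcome to covariates available without MBS linkage: age, SEIFA, and comorbidity count if it is taken from the consultation record. The protocol does not state the source of the comorbidity count, so it should be stated and checked for the same dependence.
- Run the model with prior GP use as a sensitivity analysis in MBS consenters, and report the survey score for responders with and without MBS consent side by side.

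No change to the GP-use outcome is called for on this ground.

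The cost is wording only, with no new data. The one small loss is that the main survey-outcome model no longer adjusts for prior GP use; the sensitivity analysis shows whether that matters among consenters.
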